10 STATISTICAL CONSIDERATIONS

10.1 Study Hypotheses

The study does not include formal hypothesis testing for the three primary endpoints.

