10.5 Final Analysis Plan

10.5.1 General Considerations

The SAP, which includes more technical and detailed elaboration of the principal features stated in the protocol, will be prepared separately and finalized before the interim analysis.

Safety will be assessed by estimating the occurrence of Grade 2 or higher treatment-emergent AEs in the IV bacteriophage therapies compared to placebo through Day 30 ± 7 days.

Microbiological activity will be assessed by estimating changes in $\log_{10} P. aeruginosa$ CFU/mL (total and each morphology) in sputum cultures from baseline through Day 30 ± 7 days.

The benefit to risk profile will be assessed by comparing the DOOR of IV bacteriophage arms and placebo arm through Day $8 + 3$ days. The DOOR will be analyzed by estimating the DOOR probability (Section 10.5.5), (i.e., the probability of a randomly selected subject having a better DOOR if assigned to receive an IV bacteriophage therapy compared to placebo).

All statistical calculations will be performed using up-to-date versions of SAS version 9.4 or higher (SAS Institute Inc., Cary, NC, USA) or language and environment for statistical computing 3.6.1 or higher (R Foundation for Statistical Computing, Vienna, Austria), unless otherwise specified. All PK analyses will be performed using NONMEM version 7.3 or higher (ICON Development Solutions, [name]). For continuous variables, summary statistics will include sample size, mean, SD, median, quartiles, minimum, and maximum values. Frequencies and percentages will be calculated for categorical variables. All reported confidence intervals will be two-sided 95%. Graphical displays will be produced.

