10.5.5 Analysis of Primary Endpoints

Grade 2 or higher treatment-emergent AEs will be summarized descriptively. The type of AE, number of events (n) and number (%) of subjects with events in each arm will be tabulated. The type of AE, number of AEs and the number (%) of subjects with events will be presented by system organ class (SOC), HLT, and preferred term. Subjects are counted once in each SOC, HLT, and preferred term. The difference in proportion of the number (%) of subjects with events between IV bacteriophage and placebo arms will be calculated with the corresponding exact 95% confidence interval.

Changes in \log_{10} *P. aeruginosa* CFU/mL (total and each morphology) in quantitative sputum cultures from administration of IV bacteriophages through Day 30 (\pm 7 days), Visit 7, will be summarized descriptively. Descriptive statistics will be presented by arms. The difference in mean change between IV bacteriophage and placebo arms will be estimated with the corresponding 95% confidence interval (\log_{10} -transformed and original scales). Area Under Curve (AUC) calculated using the trapezoidal rule will be used to summarize \log_{10} *P. aeruginosa* CFU/mL over the time. The difference in AUC between IV bacteriophage and placebo arms will be calculated with the corresponding 95% confidence interval.

The DOOR will be summarized by estimating the DOOR probability, using the equation

$$\text{DOOR probability} = \Pr[\text{DOOR}_{\text{IV}} > \text{DOOR}_{\text{P}}] + \frac{1}{2} \Pr[\text{DOOR}_{\text{IV}} = \text{DOOR}_{\text{P}}],$$

where DOOR_{IV} and DOOR_{P} are the DOOR for bacteriophage and placebo arms, respectively, and $\Pr[\text{DOOR}_{\text{IV}} > \text{DOOR}_{\text{P}}]$ is the proportion of a DOOR from IV bacteriophage dose exceeding a DOOR from placebo and $\Pr[\text{DOOR}_{\text{IV}} = \text{DOOR}_{\text{P}}]$ is the proportion of two DOOR outcomes being same. The corresponding 95% confidence interval will be calculated.

In addition, the DOOR will be analyzed as follows: DOOR distribution by arms, cumulative difference (point estimate and confidence band) in DOOR categories for bacteriophage vs. placebo, point estimate and confidence interval of difference in mean partial credit vs. placebo, and DOOR distribution for bacteriophage vs. placebo arm.

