## 4.5. Primary Endpoint Variables

The three primary objectives are as follows: (1) the safety of a single dose of IV bacteriophage therapy in clinically stable CF subjects with *P. aeruginosa* in expectorated sputum, (2) the microbiological activity of a single dose of IV bacteriophage therapy in clinically stable CF subjects with *P. aeruginosa* in expectorated sputum, and (3) the benefit to risk profile of a single dose of IV bacteriophage therapy in clinically stable CF subjects with *P. aeruginosa* in expectorated sputum.

The safety endpoint will be measured by the number of Grade 2 or higher treatment-emergent AEs through Day  $30 \pm 7$ . Safety will also be assessed through the incidence of treatment-emergent adverse events (TEAEs), on-therapy SAEs, and AEs leading to premature discontinuation. Adverse events will be graded according to the Common Terminology Criteria for Adverse Events (CTCAE) Version 5.0, November 2017 ([https://ctep.cancer.gov/protocoldevelopment/electronic\\_applications/ctc.htm#ctc\\_50](https://ctep.cancer.gov/protocoldevelopment/electronic_applications/ctc.htm#ctc_50)). Details about adverse event grading and determination of relationship to study product can be found in the protocol, Section 8.1.1.1.

Clinical laboratory results, including chemistry, hematology, and liver function tests, will also be graded according to the CTCAE scale. Clinical chemistry parameters include serum creatinine, blood urea nitrogen (BUN), glucose, sodium, potassium, chloride, bicarbonate, and calcium. Hematology parameters include complete blood count with red blood cell (RBC) count, hemoglobin, hematocrit, total white blood cell (WBC) count with differential counts, and platelet count. Liver function tests include aspartate aminotransferase (AST), alanine aminotransferase (ALT), alkaline phosphatase, total bilirubin, lactate dehydrogenase, albumin, and total protein. Only AST, ALT, and total bilirubin are collected at Screening. Clinical chemistry, hematology, and liver function tests will be performed at baseline and at follow-up visits occurring on Days 2, 5, 8, 12 (Stage 1 only), and 30. Refer to Section 3.3.2 for the definition of baseline.

The microbiological activity endpoint will be measured based on the change in  $\log_{10}$  *P. aeruginosa* colony counts after administration of IV bacteriophages/placebo. Sputum collection for measuring colony counts will occur at baseline and at follow-up visits occurring on Days 2, 5, 8, and 30.

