#### 8.1.2. Microbiological Activity Analysis

Changes in *P. aeruginosa* CFU/mL in quantitative sputum cultures through Day  $30 \pm 7$  and the corresponding 95% CI for the change from baseline will be summarized by treatment group in [Table 19](#) and changes in  $\log_{10}$  *P. aeruginosa* CFU/mL will be summarized in [Table 20](#). The difference in  $\log_{10}$ -transformed and original scale mean change in *P. aeruginosa* colony counts between IV bacteriophage and placebo arms, along with the corresponding 95% CIs, will be presented in [Table 21](#). A forest plot of the differences in *P. aeruginosa* colony counts is presented in [Figure 6](#) and a forest plot of the differences in  $\log_{10}$  *P. aeruginosa* colony counts is presented in [Figure 7](#). The area under the curve (AUC) calculated using the trapezoidal rule will be used to summarize  $\log_{10}$  *P. aeruginosa* CFU/mL over time. Linear trapezoidal rule will be used to calculate AUC. Area under the curve will only be calculated for subjects with non-missing colony count data from baseline through Day 30. Area under the curve of  $\log_{10}$  *P. aeruginosa* CFU/mL colony counts by treatment group will be presented in [Table 23](#). The difference in AUC between IV bacteriophage and placebo arms and the corresponding 95% CI will be calculated in [Table 24](#). The 95% CI will be obtained from Welch's t-test.

A boxplot including the median, 25th percentile, and 75th percentile of colony counts over time by treatment group will be presented in [Figure 5](#). A listing of individual colony counts will be presented in [Listing 10](#) and a listing of *P. aeruginosa* morphotypes results will be presented in [Listing 11](#).

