#### 8.1.3.1. Intention-to-Treat (ITT) Analysis of DOOR using Inverse Probability Weighting

Intention-to-treat analysis requires that all randomized subjects be included in the analysis. However, missing data is prone to happen in clinical trials due to missing scheduled visits or loss to follow-up for example. In this case, analysis that is only based on complete data may be biased if the excluded subjects are systematically different from those included. IPW is one approach commonly used to reduce this bias under a MAR assumption. This is achieved by weighting complete cases with the inverse of their probability of being a complete case. While subjects missing the DOOR are excluded from the analysis per se, they may still inform the fitting of the logistic regression model used to provide predictions of the probability of completeness which are used to calculate the weights.

Specifically, let  $Y_i$  represent the outcome of interest (DOOR),  $X_i$  represent the covariates of interest,  $Z_i$  represent any other variables measured in the data but not used in the analysis model. For the IPW approach, we first define the missingness model to estimate the weights ( $w_i$ ) using a logistic regression model with outcome  $L$  and covariates taken from set  $(X, Z)$  where  $L_i$  is defined as 1 if DOOR data is complete (not missing) and 0 otherwise. Through this model, we obtain the fitted probabilities of each subject being complete, denoted as  $\pi_i$ .

The DOOR probability can then be calculated using DOOR at Day 8 as the outcome following the algorithm below:

1. Name DOOR from the group that received placebo “sample 1” and the DOOR score ranks from the group that received IV bacteriophage “sample 2”. Rename weights from sample 1 as  $w_{1i}$  and weights from sample 2 as  $w_{2i}$ .
2. Take the first observation in sample 2. If an observation in sample 2 has a smaller DOOR score rank than an observation in sample 1, then that observation in sample 2 gets an indicator of value of 1. Otherwise, if the observation in sample 2 is equal to the observation in sample 1, the observation in sample 2 gets an indicator value of  $\frac{1}{2}$ .
3. Let  $\pi_{1i}$  be the fitted probability of being complete for each observation in sample 1 and  $\pi_{2i}$  be the fitted probability for being complete for each observation in sample 2 obtained from the logistic regression model with an indicator for having non-missing DOOR score rank as the outcome.

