Notes: Difference calculated as Placebo – IV Bacteriophage. Nb=number of subjects in the ITT population who received IV bacteriophage within the subgroup category. Np=number of subjects in the ITT population who received placebo within the subgroup category. Denominator for percentages is the total number of IV bacteriophage subjects in the ITT population for nb and the total number of placebo subjects in the ITT population for np.

a The 95% CI for the difference in means is computed from Welch's t-test.

**Table 23: AUC of  $\log_{10} P. aeruginosa$  Total Colony Counts in Quantitative Sputum Cultures Over Time – ITT Population, Stage 2a and 2b**

Time Point	Treatment Group	AUC				
		n	Mean	SD	Median	Min, Max
Day 1 Post-infusion	Selected Dose (N=X)	x	xx.x	xx.x	xx.x	xx.x, xx.x
	Placebo (N=X)	x	xx.x	xx.x	xx.x	xx.x, xx.x
Day 2	Selected Dose (N=X)	x	xx.x	xx.x	xx.x	xx.x, xx.x
	Placebo (N=X)	x	xx.x	xx.x	xx.x	xx.x, xx.x
Day 5	Selected Dose (N=X)	x	xx.x	xx.x	xx.x	xx.x, xx.x
	Placebo (N=X)	x	xx.x	xx.x	xx.x	xx.x, xx.x
Day 8	Selected Dose (N=X)	x	xx.x	xx.x	xx.x	xx.x, xx.x
	Placebo (N=X)	x	xx.x	xx.x	xx.x	xx.x, xx.x
Day 30	Selected Dose (N=X)	x	xx.x	xx.x	xx.x	xx.x, xx.x
	Placebo (N=X)	x	xx.x	xx.x	xx.x	xx.x, xx.x
Maximum	Selected Dose (N=X)	x	xx.x	xx.x	xx.x	xx.x, xx.x
	Placebo (N=X)	x	xx.x	xx.x	xx.x	xx.x, xx.x

Notes: N=Number of subjects in the ITT Population in Stage 2a and 2b.

n=Number of subjects in the ITT Population with non-missing colony counts at the time point of interest.

SD=Standard Deviation

AUC will be calculated using the linear trapezoidal rule as the area under the curve between baseline and the given time point.

**Table 24: Difference in AUC of  $\log_{10} P. aeruginosa$  Total Colony Counts in Quantitative Sputum Cultures – ITT Population, Stage 2a and 2b**

[Implementation note: ‘Selected IV Bacteriophage Dose’ will be replaced with the dose chosen by the interim analysis. The 95% CI for the difference in means is computed from Welch’s t-test].

Time Point	Treatment Group	Difference in AUC	95% CI a
Day 1 Post-infusion	Selected IV Bacteriophage Dose (N=X)	xx	xx.x, xx.x
Day 2	Selected IV Bacteriophage Dose (N=X)	xx	xx.x, xx.x
Day 5	Selected IV Bacteriophage Dose (N=X)	xx	xx.x, xx.x
Day 8	Selected IV Bacteriophage Dose (N=X)	xx	xx.x, xx.x
Day 30	Selected IV Bacteriophage Dose (N=X)	xx	xx.x, xx.x
Maximum	Selected IV Bacteriophage Dose (N=X)	xx	xx.x, xx.x

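### The log10 CFU AUC is a raw area computed only for subjects with a complete sample series, which discards subjects and can cost precision; the size depends on SDs the documents do not give

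*SAP*

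**What the plan says.** Protocol 10.5.5 lists the AUC under the analysis of primary endpoints: "The difference in AUC between IV bacteriophage and placebo arms will be calculated with the corresponding 95% confidence interval". SAP 8.1.2 specifies the linear trapezoidal rule on log10 CFU/mL and a Welch interval for the difference between arms, and sets the inclusion rule: "Area under the curve will only be calculated for subjects with non-missing colony count data from baseline through Day 30".

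The notes to SAP Tables 23 and 24 define the quantity: "AUC will be calculated using the linear trapezoidal rule as the area under the curve between baseline and the given time point". Neither the SAP nor its addendum on undetectable counts mentions baseline subtraction, baseline adjustment, division by elapsed time, or a choice between actual and nominal days.

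The note to Table 23 describes the denominator differently from 8.1.2: "n=Number of subjects in the ITT Population with non-missing colony counts at the time point of interest". That is a per-visit count, not a complete-series count. The addendum's AUC tables repeat it.

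SAP 6.5 confines missing-data methods to DOOR. In SAP 8.1.3.1 the plan gives its own reason for protecting DOOR: "analysis that is only based on complete data may be biased if the excluded subjects are systematically different from those included".

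**The concern.** The AUC tables are labelled ITT, yet one absent sample removes a subject from a summary in the primary-endpoint section. Missing samples are plausible. Two collections fall on the dosing day, each needing at least 2 mL (Protocol 7.2.1), and in Stage 2 the Day 8 visit is virtual, with a kit supplied to the subject (Protocol 6.4).

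A raw area also carries each subject's habitual bacterial load into the comparison, and if actual days are used it carries the length of follow-up too. Both add variance unrelated to treatment. With 20 to 25 subjects per arm and conclusions resting on confidence intervals, lost subjects and avoidable variance widen the AUC interval. If missing samples are related to response, the complete-case set is also a selected one.

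**Working it through.** The documents state no SD, effect size or precision for the AUC, so there is no planned figure to reproduce. Values marked *assumed* are not in the documents.

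**1. Number of samples.** SAP 4.5 states: "Sputum collection for measuring colony counts will occur at baseline and at follow-up visits occurring on Days 2, 5, 8, and 30". That is five. SAP Table 23 adds a Day 1 post-infusion row, making six.

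**2. Subjects kept.** With independent missingness m per sample (*assumed*), the fraction with a complete series is (1 − m)^6.

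| m | complete | dropped | left of 20 | left of 25 |
|---|---|---|---|---|
| 2% | 0.886 | 11% | 17.7 | 22.1 |
| 5% | 0.735 | 26% | 14.7 | 18.4 |
| 10% | 0.531 | 47% | 10.6 | 13.3 |

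Counting only the five samples of SAP 4.5, the losses at 5% and 10% are 1 − 0.95^5 = 23% and 1 − 0.90^5 = 41%. With six samples, ignoring the change in t quantile, the interval widens by √(1/0.735) = 1.17 at 5% and √(1/0.531) = 1.37 at 10%.

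**3. Weight of each sample.** Take samples at 0, 0.1, 1, 4, 7 and 29 days after dosing (nominal; 0.1 approximates the 2-hour sample). The trapezoid weights are 0.05, 0.5, 1.95, 3, 12.5 and 11, which sum to 29. The Day 1 post-infusion sample carries 0.5/29 = 1.7% of the area. Days 8 and 30 together carry 23.5/29 = 81%.

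**4. Follow-up time.** Day 30 ± 7 is 22 to 36 days after dosing. At an *assumed* level of 5 to 7 log10, a 7-day shift in the last visit moves the raw area by 35 to 49 log10-days. A sustained 1 log10 effect moves it by about 29. This applies only if actual days are used. With nominal days, dividing by time changes nothing.

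**5. Standardised effect, nominal days.** Let sb and sw be the between- and within-subject SDs (*assumed*). The squared weights sum to 290.3, and 290.3/29² = 0.345. A sustained 1 log10 effect on every post-dose sample gives a time-averaged difference of 28.95/29 = 0.998.

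- Raw area: d = 0.998/√(sb² + 0.345 sw²)
- Time-averaged area minus baseline: d = 0.998/(sw √1.342)
- Baseline as covariate: residual variance = (sb² + 0.345 sw²) − (sb² + 0.0017 sw²)²/(sb² + sw²)

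For sb/sw = 1.0/0.7 these give 0.998/1.081 = 0.92, 0.998/0.811 = 1.23 and 0.998/0.705 = 1.42. A simulation with 60,000 subjects per arm agrees (0.93, 1.22, 1.42).

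**6. Simulated range.** The table assumes a mean of 7 log10 and a sustained 1 log10 effect. Full windows means visits uniform over their windows, with actual days used.

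| sb/sw | days | raw | minus baseline | covariate | raw ÷ minus baseline |
|---|---|---|---|---|---|
| 1.5/0.5 | nominal | 0.65 | 1.73 | 1.78 | 0.38 |
| 1.0/0.5 | nominal | 0.96 | 1.72 | 1.87 | 0.56 |
| 1.0/0.7 | nominal | 0.93 | 1.22 | 1.42 | 0.76 |
| 1.0/1.0 | nominal | 0.85 | 0.86 | 1.08 | 0.99 |
| 0.5/1.0 | nominal | 1.29 | 0.86 | 1.35 | 1.50 |
| 1.5/0.5 | full windows | 0.55 | 1.72 | 1.80 | 0.32 |
| 1.0/0.7 | full windows | 0.67 | 1.24 | 1.41 | 0.54 |
| 1.0/1.0 | full windows | 0.65 | 0.86 | 1.08 | 0.76 |

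Over all scenarios, including a mean of 6 log10, a narrower timing spread and an effect gone by Day 30, raw ÷ minus baseline ran from 0.31 to 1.50. Raw ÷ covariate-adjusted ran from 0.30 to 0.96. With full windows it ran from 0.30 to 0.64.

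**The case against.** The strongest reply is that little depends on this summary. The named endpoint is change from baseline to Day 30, analysed in SAP Tables 20 and 21 with baseline subtracted and subjects kept visit by visit. Protocol 10.1 adds: "The study does not include formal hypothesis testing for the three primary endpoints". The AUC feeds neither DOOR nor the sample size. All of that stands, and it limits the consequence to the AUC interval.

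It is also true that randomisation protects the raw area from bias due to baseline differences. Leaving out baseline adjustment costs precision only; any bias would have to come from the complete-case rule.

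Two stronger readings are tempting and are not supported:

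- A reader might infer that the raw area halves the standardised effect. That holds for some SDs, such as 1.0/0.5, but the documents give none. At 1.0/1.0 with nominal days nothing is lost against plain subtraction, and at 0.5/1.0 the raw area does better than subtraction.
- A reader might infer that the best responders are removed because their counts become undetectable. The addendum's primary analysis sets undetectable counts to the limit of detection, so those subjects stay in. They drop out only in its sensitivity version. Of the five Stage 2a subjects with no calculable change at the interim, three were undetectable at baseline and two at every later time point. The addendum also notes that an undetectable result may reflect an invalid sample.

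The missingness rates are assumptions; actual sample completeness may be better.

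**Conclusion.** The concern holds as a weakness of a supporting analysis. The complete-series rule, the raw area and the absence of any missing-data method are explicit or follow from the text. The rule also conflicts with the Table 23 note, so two programmers could produce different tables.

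The loss of subjects rests on assumed independent missingness across six samples. In the addendum's sensitivity version any undetectable sample adds to that loss. The loss of standardised effect depends on unstated SDs and on an unstated choice of actual or nominal days: half or more in the unfavourable cases, little or none against subtraction when the SDs are similar and days are nominal. Conclusions from change from baseline and from DOOR do not change.

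**What to change.** Amend SAP 8.1.2 and the notes to Tables 23 and 24, with the matching addendum Tables 9 to 12, as follows:

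1. Compute the trapezoid over the available samples for every subject with a baseline and an end-of-interval sample, interpolating linearly across missing interior samples.
2. Divide by actual days from baseline, giving a time-averaged log10 CFU/mL, and state that actual days are used.
3. Compare arms in a linear model with baseline log10 CFU as a covariate, in place of the unadjusted Welch interval. Plain subtraction is not recommended, because it was worse than the raw area when within-subject variation dominated and days were nominal. The covariate version was never worse in the scenarios run.
4. Make the Table 23 n note count the subjects who meet rule 1.

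The cost is a few sentences and minor reprogramming. The method assumes linearity across missing interior samples. In the sensitivity version this would place an interior undetectable sample on the line between its neighbours, which should be stated. Subjects lacking a baseline or final sample are still excluded.

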### 8.1.3. Benefit to Risk Profile Analysis Using DOOR

Each subject will have a composite DOOR rank assigned to them based on the presence or absence of SAEs related to study product and the reduction in  $\log_{10} P. aeruginosa$  CFU/mL. DOOR rank will be determined according to the definition in Section 3.3.1.

DOOR probability, which is defined by:

$$DOOR\ probability = Pr[DOOR_2 > DOOR_1] + \frac{1}{2} Pr[DOOR_2 = DOOR_1],$$

will be estimated using the Wilcoxon-Mann-Whitney statistic, correcting for ties and divided by the product of the placebo and IV bacteriophage group sample sizes, where

- DOOR2 and DOOR1 are the DOOR for IV bacteriophage and placebo arms, respectively
- Pr[DOOR2 > DOOR1] is the probability of a DOOR from IV bacteriophage dose being more desirable than a DOOR from placebo, and
- Pr[DOOR2 = DOOR1] is the probability that the DOOR outcomes in IV bacteriophage and placebo are the same.

The corresponding two-sided 95% CI will be calculated using the method described in Halperin et al. [2] for the incorporation of IPW described in Section 8.1.3.1. Note that all CIs are two-sided.

The 95% CI by Halperin et al. [2] will be calculated in the following manner:

- $n_1$ : number of subjects in ITT population randomized to placebo
- $n_2$ : number of subjects in ITT population randomized to IV bacteriophage
- $W$ : Wilcoxon-Mann-Whitney statistic for ordinal outcomes, corrected for ties
- $\zeta$ : DOOR probability
- $\hat{\zeta}$ : An unbiased estimator of  $\zeta$ ,  $\hat{\zeta} = W/(n_1 n_2)$
- $V$ : The variance of the DOOR probability. Correcting for ties, the formula for the variance of the DOOR Probability, as described in Halperin et al. [2], is:

$$\hat{V} = Var(\zeta) = \frac{1}{n_1 n_2} [n_1 + n_2 + 1 - (n_1 + n_2 - 2)\theta] \zeta (1 - \zeta)$$

where

$$\theta = \frac{[(n_1 + n_2 - 2)\zeta - (n_2 - 1)A - (n_1 - 1)B]}{(n_1 + n_2 - 2)\zeta(1 - \zeta)}$$

To obtain an estimator  $\hat{\theta}$  of  $\theta$ , the following formulas will be used for A and B, respectively:

$$\hat{A} = \hat{A}_1 - \frac{1}{n_2 - 1} \sum_{i=1}^{D-1} p_{1i} \left[ q_{2i} \sum_{j=i+1}^D p_{2j} - \left( \sum_{j=i+1}^D p_{2j} \right)^2 \right] - \frac{1}{4(n_2 - 1)} \sum_{i=1}^D p_{1i} p_{2i} q_{2i}$$

where

$$\hat{A}_1 = \sum_{i=1}^{D-1} p_{1i} \left[ \sum_{j=i+1}^D p_{2j} + \frac{p_{2i}}{2} \right]^2 + \frac{p_{1D} p_{2D}^2}{4}$$

and

$$\hat{B} = \hat{B}_1 - \frac{1}{n_1 - 1} \sum_{j=2}^D p_{2j} \left[ q_{1j} \sum_{i=1}^{j-1} p_{1i} - \left( \sum_{i=1}^{j-1} p_{1i} \right)^2 \right] - \frac{1}{4(n_1 - 1)} \sum_{j=1}^D p_{2i} p_{1i} q_{1i}$$

where

$$\hat{B}_1 = \sum_{j=2}^D p_{2j} \left[ \sum_{i=1}^{j-1} p_{1i} + \frac{p_{1j}}{2} \right]^2 + \frac{p_{11}^2 p_{21}}{4}$$

In the equations for A and B above, D is the number of DOOR outcome ranks in the dataset;  $p_{1i}$ , for  $i = 1, 2, \dots, D$ , represents the proportion of subjects randomized to placebo with the  $i^{\text{th}}$  rank category of DOOR;  $p_{2j}$ , for  $i = 1, 2, \dots, D$ , represents the proportion of subjects randomized to IV Bacteriophage with the  $j^{\text{th}}$  value of DOOR; and  $q = 1 - p$  in general.

Additionally, the equation for an unbiased estimate of  $\zeta(1 - \zeta)$  is given by:

$$\frac{(n_1 n_2 - n_1 - n_2 + 2)\hat{\zeta} - n_1 n_2 \hat{\zeta}^2}{(n_1 - 1)(n_2 - 1)} + \frac{\hat{A}}{n_1 - 1} + \frac{\hat{B}}{n_2 - 1}$$

After substituting the values of A, B and  $\zeta(1 - \zeta)$  in the equation  $\theta$  to obtain an estimate  $\hat{\theta}$  of  $\theta$ ,  $\theta$  is defined as follows: If  $\hat{\theta} < 0$  then  $\theta = 0$ , if  $\hat{\theta} > 1$  then  $\theta = 1$ , otherwise  $\hat{\theta} = \theta$ .

We now compute the pivotal quantity  $Z_H^2 = (\hat{\zeta} - \zeta)^2 / \hat{V}$ .

$$\gamma = (n_1 + n_2 - 1) - (n_1 + n_2 - 2)\hat{\theta}$$

The CI is obtained as the solution set in  $\zeta$  of the quadratic inequality:

$$n_1 n_2 \frac{(\hat{\zeta} - \zeta)^2}{\gamma \zeta (1 - \zeta)} \leq \chi^2(1, 1 - \alpha)$$

Let,  $C = \gamma \chi^2(1, 1 - \alpha) / (n_1 n_2)$ . The CI is given as:

$$\frac{C + 2\hat{\zeta} \pm [C^2 + 4C\hat{\zeta}(1 - \hat{\zeta})]^{1/2}}{2(C + 1)}$$

The superiority of IV bacteriophage vs placebo is concluded if the lower bound of the 95% CI for the DOOR probability is larger than 50%.

Due to the presence of missing data, IPW will be used to handle missing data. For the sensitivity analysis of DOOR, IPW method will be used (see Section 8.1.3.1).

The DOOR will be analyzed as follows:

- DOOR probability with corresponding 95% CI calculated using the method described in Halperin et al. [2] calculated using the greatest reduction in *P. aeruginosa* CFU/mL by Day 8 (Table 26).
- DOOR categories distribution by treatment group through Day 8 + 3 (Table 28).

- Cumulative proportions of DOOR categories through Day 8 + 3 for IV bacteriophage vs. placebo with cumulative DOOR probabilities and corresponding 95% CI ([Table 31](#)). This analysis compares the DOOR probability from the following dichotomizations of DOOR: first by calculating the dichotomized DOOR probability comparing those with DOOR rank = 1 to DOOR ranks 2, 3, and 4 pooled together, then DOOR rank 1 and 2 compared to DOOR rank 3 and 4, and finally comparing DOOR ranks 1, 2, and 3 to DOOR rank 4.
- Sequential dichotomization of DOOR will be presented in [Figure 12](#). Cumulative probabilities will be calculated using the following dichotomizations: rank 1 vs ranks 2, 3, and 4; ranks 1 and 2 vs ranks 3 and 4; and ranks 1, 2, and 3 vs rank 4.
- Comparison of each of the components of the DOOR between the IV bacteriophage and placebo arms through Day 8 with 95% CI, summarized by DOOR probability and 95% CI ([Table 33](#)). For the SAE component of DOOR the dichotomized DOOR probability will be calculated using ‘No SAE’ = rank 1 and ‘SAE’ = rank 2. For the log10 reduction component of DOOR the dichotomized DOOR probability will be calculated using ‘>2 log10 reduction in *P. aeruginosa* CFU/mL’ = rank 1, ‘1-2 log10 reduction in *P. aeruginosa* CFU/mL’ = rank 2, and ‘<1 log10 reduction in *P. aeruginosa* CFU/mL’ = rank 3.
- Forest plot of probabilities of DOOR and its components at Day 8 + 3 and corresponding 95% CI calculated using the method in Halperin et. al. [2] ([Figure 10](#)).
- Point estimate and CI of difference in mean partial credit vs. placebo through Day 8 and corresponding 95% CI ([Table 32](#)). The 95% CI will be calculated using Welch’s t-test. The partial credit analysis will be calculated assigning a grading key to each of the DOOR categories. The grading keys used will be the following: A: (DOOR rank 1 = 100, rank 2 = 100, rank 3 = 100, rank 4 = 0), B: (rank 1 = 100, rank 2 = 100, rank 3 = 0, rank 4 = 0), C: (rank 1 = 100, rank 2 = 0, rank 3 = 0, rank 4 = 0). For each scenario, the mean and SD of these partial credit scores will be provided for each treatment group and corresponding scenario.
- Difference in means of partial credit score by time point ([Figure 13](#)).

A listing of individual DOOR response data will be presented in [Listing 12](#).

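### The DOOR confidence interval in SAP 8.1.3 runs its rank index against the DOOR probability; coded as printed, it is far too narrow for estimates of about 0.53 to 0.88

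*SAP*

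**What the plan says.** SAP 3.3.1 numbers the four outcomes from Rank 1 (most desirable) to Rank 4 (related SAE, least desirable). Section 8.1.3 adopts that numbering: "DOOR rank will be determined according to the definition in Section 3.3.1".

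The DOOR probability, zeta, is defined by desirability. Its first term "is the probability of a DOOR from IV bacteriophage dose being more desirable than a DOOR from placebo", with half credit for ties. Step 2 of the weighting algorithm in 8.1.3.1 scores a win in the same direction: "If an observation in sample 2 has a smaller DOOR score rank than an observation in sample 1".

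The interval is built from A and B. Their placebo proportions are indexed by the i-th "rank category of DOOR", and "D is the number of DOOR outcome ranks in the dataset". A adds phage proportions over j > i; B adds placebo proportions over i < j.

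The supporting analyses also number from best. For Table 33, "the dichotomized DOOR probability will be calculated using ‘No SAE’ = rank 1 and ‘SAE’ = rank 2"; Table 31 starts by "comparing those with DOOR rank = 1 to DOOR ranks 2, 3, and 4 pooled together".

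Superiority "is concluded if the lower bound of the 95% CI for the DOOR probability is larger than 50" per cent. The footnote to Table 26 repeats the rule.

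**The concern.** With Rank 1 best, a higher phage index is a worse phage outcome. The printed sums in A and B therefore count phage losses as wins and are second moments for 1 − zeta. The formulas for theta and for the estimate of zeta(1 − zeta) then combine them with zeta itself. No sentence tells the programmer to reverse the ranks.

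Stage 2 was sized on the precision of the DOOR probability (SAP section 5), and superiority is read from this lower limit. Tables 31 and 33 use the same interval. The limit-of-detection supplement (section 2.1) sends its DOOR analyses back to the same methods. An interval that is too narrow would turn small differences in favour of phage into superiority.

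**Working it through.** **The plan's own interval.** SAP section 5 gives 51% to 89% at zeta = 0.70; the protocol (10.2) ties this to 20 per arm. The tie-free Wilcoxon null variance gives 0.70 ± 1.96 × √(41/(12 × 400)) = 0.70 ± 0.181, or 51.9% to 88.1%. A t quantile on 38 df gives 51.3% to 88.7%. The figure is reproduced to within a point and is 0.38 wide. The documents do not give the variance formula used.

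**Formulas (SAP 8.1.3), n1 = n2 = 20.**
- theta = [38·zeta − 19A − 19B] / [38·zeta(1 − zeta)], cut to the range 0 to 1
- gamma = 39 − 38·theta
- C = 3.841·gamma/400
- limits = {C + 2·zeta ± √[C² + 4C·zeta(1 − zeta)]} / {2(C + 1)}

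**Worked case.** Counts in Ranks 1 to 4: placebo 1/3/16/0, phage 2/5/13/0. So p1 = (0.05, 0.15, 0.80, 0) and p2 = (0.10, 0.25, 0.65, 0).

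Zeta-hat, by smaller rank number: 0.05 × 0.05 + 0.15 × 0.225 + 0.80 × 0.675 = 0.57625.

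First moment behind A as printed: 0.05 × 0.95 + 0.15 × 0.775 + 0.80 × 0.325 = 0.42375. This is 1 − zeta-hat.

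| | A indexed as printed | Least to most desirable |
|---|---|---|
| Leading term of A | 0.05 × 0.95² + 0.15 × 0.775² + 0.80 × 0.325² = 0.2197 | 0.05 × 0.05² + 0.15 × 0.225² + 0.80 × 0.675² = 0.3722 |
| A, B after correction | 0.2164, 0.2356 | 0.3689, 0.3881 |
| Estimate of zeta(1 − zeta) | 0.2337 | 0.2498 |
| theta | 13.31/8.88 = 1.50, cut to 1 | 7.515/9.49 = 0.792 |
| gamma, C | 1, 0.0096 | 8.91, 0.0856 |
| 95% CI | 0.527 to 0.624 | 0.431 to 0.709 |

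Putting zeta, A and B all on the rank scale and mirroring the result also gives 0.43 to 0.71.

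**Further cases, 20 per arm.**

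| Placebo vs phage | zeta-hat | As printed | Aligned |
|---|---|---|---|
| 2/4/14/0 vs 6/9/5/0 | 0.7325 | 0.69–0.77 (theta 3.99 before the cut) | 0.57–0.85 |
| 2/4/14/0 vs 2/5/13/0 | 0.52 | 0.45–0.60 | 0.37–0.67 |
| 2/5/13/0 vs 1/3/16/0 | 0.42 | 0.20–0.68 | 0.29–0.57 |
| 0/2/18/0 vs 14/6/0/0 | 0.985 | 0.71–0.999 | 0.94–0.996 |
| Table 31 type: Rank 1 in 2/20 vs 4/20 | 0.55 | 0.501–0.598 | 0.43–0.66 |
| Table 33 type: related SAE in 2/20 vs 0/20 | 0.55 | 0.501–0.598 | 0.467–0.631 |

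**Threshold for superiority.** The lower limit exceeds 0.5 when zeta-hat > 0.5 and (zeta-hat − 0.5)² > C/4. With theta = 1, gamma = 1, so the threshold is 0.5 + ½√(3.841/400) = 0.549 at 20 per arm and 0.5 + ½√(3.841/625) = 0.539 at 25. In simulation the printed coding cut theta to 1 in at least 99.9% of trials with zeta-hat 0.55 to 0.90. The smallest aligned estimate called superior in those simulations was 0.625 (n = 20) or 0.600 (n = 25).

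**Width.** Median ratio, printed to aligned:

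| zeta-hat | n = 20 | n = 25 |
|---|---|---|
| 0.51–0.53 | 0.52 | 0.51 |
| 0.53–0.55 | 0.37 | 0.34 |
| 0.55–0.60 | 0.34 | 0.30 |
| 0.60–0.88 | 0.30–0.33 | 0.27–0.30 |
| 0.92–0.95 | 2.1 | 2.1 |

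Below 0.50 the printed interval is too wide (1.7 at 0.40–0.45).

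**Identical arms, lower limit above 0.5 as printed.** The documents give no category distribution, so these are assumptions (40,000 trials each).

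| Ranks 1–4 | n = 20 | n = 25 |
|---|---|---|
| .33/.33/.34/0 | 28.5% | 31% |
| .20/.30/.48/.02 | 28% | 31% |
| .10/.25/.65/0 | 26% | 29% |
| .05/.15/.80/0 | 23% | 25% |
| .10/.10/.80/0 | 22% | 25% |
| .02/.08/.90/0 | 19% | 21% |
| .01/.04/.95/0 | 12% | 15% |

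Aligned, the rate is 0.1 to 2.4%. At four assumed alternatives with true zeta 0.68 to 0.69, printed coverage is 44–51% (n = 20) or 40–47% (n = 25), against 95–96% aligned. Median width at n = 20 is 0.09 against 0.25–0.29.

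**The case against.** The strongest reply is that the failing version is a mixed reading. It orders zeta by desirability and A and B by raw rank number within one calculation. Section 8.1.3 explains the greater-than sign as more desirable, and on that ordering the sums in A and B are right. The formulas are algebraically correct when a higher index is better. A careful programmer, or one working from the cited method, would get the right interval, and nobody has shown that the wrong coding is in use.

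This stands as far as it goes: the fault is conditional, and the documents cannot show which version was programmed. It does not remove the point. The greater-than sign fixes the direction of zeta only. The index of A and B is tied to the rank category, ranks come from Section 3.3.1, and the component analyses number from best. The only pseudocode covers the missingness weights.

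The plan also disclaims formal testing. It still states a superiority rule, and an interval a third of its proper width misleads as description too.

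Smaller objections are fair:
- The Table 33 example needs two related SAEs on placebo, although one related SAE already suspends enrolment and dosing.
- The planning interval comes from a different method, so its width is only a rough comparison.
- The aligned thresholds are simulation minima. Direct enumeration finds an aligned superior result at 0.6175 (n = 20) and 0.5952 (n = 25), still well above 0.549 and 0.539.

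**Conclusion.** The concern holds. Followed literally, SAP 8.1.3 gives a wrong interval for the quantity on which Stage 2 was sized. The interval is about 0.27 to 0.37 of its proper width for estimates of 0.53 to 0.88, and the superiority threshold falls to 0.549 or 0.539. Under the assumed null distributions the false-superiority rate is 12 to 31%. Truncating theta leaves a plausible-looking interval, so the error would not show itself. The point estimate is unaffected if wins are counted by desirability.

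The worked intervals and thresholds follow from the printed formulas. The rates and coverages rest on assumed category distributions and complete data with equal weights. Missing data are expected in practice: 5 of the 32 interim subjects could not contribute a DOOR.

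**What to change.** State in SAP 8.1.3 that, in both arms, index 1 is the least desirable category (Rank 4) and index D the most desirable (Rank 1). Apply the same order to the dichotomized and component analyses behind Tables 31 and 33. A consistent rank-scale calculation, mirrored at the end, is equivalent, but one convention must be written down.

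Add a program check that Σi p1i(Σj>i p2j + p2i/2) equals zeta-hat, and run it on any program already written.

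Two slips can be corrected at the same time. The printed variance has n1 + n2 + 1 where gamma has n1 + n2 − 1; the latter is right, and the interval uses gamma, so its limits do not change. The last sum in B runs over j, but its terms carry the index i.

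The cost is one sentence, the category order in the program and one check. No data or patients are affected.
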